Concussion diagnosis/history	History of TBI of any severity History of moderate, severe, or penetrating TBI as defined by DoD/VA guidelines during lifetime History of at least one MTBI sustained at least 1 month previously based on criteria of the DoD diagnostic criteria (VA/DoD) Any loss of consciousness (not to exceed 30 minutes) Any loss of memory for events immediately before or after the injury (not to exceed 1 day) Any alteration of consciousness or change in mental state (not to exceed 24 hours) Persistent post-concussive symptoms
Neuroendocrine test	Test results
Imaging records	MRI CT

If you will merge data, also indicate non-MHS data elements about research participants or relatives, employers, or household members of the research participants that you will have access to in any form or medium.

Do you believe it is possible for the MHS data to become identifiable because of triangulation, a small cell size, or any unique data element(s)?

Triangulation means using different data elements that are not themselves identifiable but that when combined can be used to identify an individual. For example, triangulation would use rank and race together to determine the identity of an individual with a particular health condition.

Small cell size means that there is only a small number of eligible individuals that satisfy the category description. Guidance for acceptable cell size is available from the Centers for Medicare and Medicaid Services. For example, the rank category of four star generals with a particular diagnosis may be less than 30, so the rank category may need to be expanded to include lower ranks.

A unique data element includes any unique features that are not explicitly enumerated in the categories of data in rows 1 – 20 of the table above (in Section 10.10), but that could be used to identify an individual. Unique data elements include characteristics that are not themselves identifying, such as the rank of general or admiral, or a race or gender, but within the context of other information could be identifiable.

Yes, I believe there is a reasonable possibility the MHS data will become identifiable

No, I believe there is no reasonable possibility the MHS data will become identifiable

Have you completed and uploaded an appropriate HIPAA document (i.e. HIPAA Authorization will be obtained or Waiver/alteration of HIPAA Authorization is being requested)?

Yes

No

N/A

10.14 Managing Data (Data Management and/or Sharing Plan) and/or Human Biological Specimens for this Study:

Include in this section the plan for acquiring data (both electronic and hard copy), access during the study, data/specimen storage and length of time stored, shipment/transmission, and the plan for storage and final disposition at the conclusion of the study. Describe any data agreements in place for accessing data within and/or outside of your institution (e.g., Data Sharing Agreement, Data Use Agreement, Business Agreements, etc.)

This study will follow best-practice standards regarding management of sensitive participant data, including personally identifiable information (PII) and protected health information (PHI). Each participant will be assigned a unique Subject ID upon consenting to the study. Each Subject ID will be a unique alphanumeric code and will not contain any personal identifiers of the participant assigned to it. Personal identifiers collected in this study include name, date of birth, address, phone number, email address, and DoD ID number. All personal identifiers will be stored separately in a secure password-protected database, and will not be linked to any clinical and/or research data collected in this study.

Electronic copies will be password protected and stored on the NHCP network, the specific server folder can be found at \\CPENFS01\Dept\$\Director Of Branch Clinics\DVBC\ADMIN\TOBI-SET\Data Management. Hard copies will be stored in a locking filing cabinet inside research office #324 located at the Intrepid Spirit Center Camp Pendleton.

A "master-list" roster of consented participants will be maintained electronically in a separate password-protected database in a secured (restricted-access) shared directory, as well as physically in a locked file cabinet inside a secured (locked) research office. This master list will include the personal identifiers described above, as well as the FITBIR GUID. This master list is the only location where personal identifiers of participants will be stored. Other records related to this study will be kept electronically in a password-protected database completely separate from the master list, and in hard copy form in a locked file cabinet separate from the master. All study records and data will be identified only by the Subject ID. The only individuals with access to the master list and to study records/data will be the PI and key research personnel. Lastly, DoD representatives will be granted access to review study records, accompanied by the PI, if requested in writing with a specific reason(s) for access.

Data will be obtained for this study at multiple time points in the following ways:

- 1) Self-report questionnaires which include standardized psychological tests, sleep measures, demographics, military information and combat exposure measures
- 2) a work performance questionnaire which will be completed, by direct supervisors regarding performance of consented participants.
- 3) Neuropsychological Assessments, which include measures of divided attention, visual searching, motor and processing speed, mental flexibility, inhibition, and verbal learning and memory.
- 4) Exercise Measures (HR, exercise log, etc.), which include wearables that measure HR, sleep data and an exercise compliance questionnaire to record exercise duration and types of exercises performed.
- 5) Physiological Assessments (Doppler, VO₂, BCTT, etc), which include measuring cerebrovascular blood flow (CBF), heart rate variability, oxygen consumption (VO₂), and isometric strength.

Data will also be verified in electronic medical records (e.g. health care utilization). Collection of this data will be handled by qualified research personnel using standardized protocols. Study records and data will be stored in hard copy form (if applicable) as well as electronically.

Data will be collected through Qualtrics, an online survey platform both on study site computers and through links sent via email to participants and supervisors. Identifying information, including PII, IP address and geo-location, will not be obtained or stored through these online surveys to maintain confidentiality. Qualtrics is FedRamp compliant and IT approved. At the completion of study data collection, all data collected will be removed from the survey platform data server. The study will own and control all data collected through these means. Only approved study team members will have access to it. In lieu on the online survey platform the measures can also be administered via paper and pencil.

A database will be developed for the purposes of storing and analyzing the study data. This database will be password-protected and housed in a limited-access shared directory on a DoD server only accessible to research personnel. Specifically, the database will be located in the following directory: \\CPENFS01\\Dept\$\\Director Of Branch Clinics\\DVBIC\\ADMIN\\TOBI-SET\\DataManagement. As described above, this database will be entirely separate from the database containing the master list, and all research data will only be identified by the GUID.

This database will have robust functionality with regards to inputting study data and analyzing/exporting relevant data points. All data collected from questionnaires will be inputted into the database by research personnel. The database will allow researchers to organize and easily analyze relevant data through the use of custom queries. More complex research questions and data analysis will be done with additional software that has advanced statistical analysis functionality (e.g. Stata, SPSS). The study database will be designed to facilitate transfer of raw data in a compatible format for such purposes. De-identified data will be transferred from the database to the study personnel for analysis. Analysis will not occur within the database structure. The data will be analyzed by the study's statistician, PI and AIs.

Hard copies of study records, including raw measurement data, participant-completed forms, and database generated datasheets, will be kept in a locked file cabinet inside a secured (locked) office. In accordance with federal policy, data hard copies will be properly destroyed six years following study closure. Data elements will be reported using the National Institute of Neurological Disorders and Stroke (NINDS) TBI Common Data Elements. If needed, new and unique data elements will be submitted to FITBIR only after grant office and IRB approval.

Data elements will be reported using the National Institute of Neurological Disorders and Stroke (NINDS) TBI Common Data Elements. If needed, new and unique data elements will be submitted to FITBIR only after IRB and grant office approval.

We will safeguard the data from becoming identifiable through the following means:

- Using strong passwords to safeguard our data
- Allowing only research personnel with access to the NHCP server to access these password protected databases.
- Storing identifiers in a separate password protected file separate from the coded data
- Transmitting data without identifiers and only through approved platforms such as DoD safe and/or via an encrypted email.
- Storing physical identifiers in a locking office with limited access in separate filing cabinets from the coded data (e.g., test packets). Keys to the filing cabinets in which data is stored will be kept in a separate locking filing cabinet.

The study researchers acknowledge that there may be information gathered through the study that may be of interest or benefit to the patient. Therefore, at the conclusion of the participant's involvement in the study, the patient will be offered a feedback session with a study investigator to go over clinical data pertaining to neuropsychological testing results and/or improvement from study treatment. Additionally, should the participant choose to share these results with their primary care manager (PCM), a study investigator will forward the relevant data to the participant's PCM with the provision of a signed release form.

10.15 Managing Data (Data Management and/or Sharing Plan) and/or Human Biological Specimens for Future Research:

If the study involves collecting, storing, or banking human specimens, data, or documents (either by the Investigator or through an established repository) for FUTURE research, address. How the specimens/data will be used, where and how data/specimens will be stored (including shipping procedures, storage plan, etc.), whether and how consent will be obtained, procedures that will fulfill subjects' request as stated in the consent, whether subjects may withdraw their data/specimens from storage, whether and how subjects may be re-contacted for future research and given the option to decline, whether there will be genetic testing on the specimens, who will have access to the data/specimens, and the linkage, the length of time that data/specimens will be stored and conditions under which data/specimens will be destroyed.

De-identified data collected during the study will be deposited into the FITBIR Informatics System, which makes the data available to the TBI research community for future analysis and research. Study participants will be informed of such information sharing at the time of consent. Subjects will have the option to remove their data from the FITBIR system. In addition to data, research resources used in the study, which are funded will be made available to the research community using the FITBIR Informatics System. Further, our staff will ensure proper and timely documentation of the methodology and procedures for data collection, useful details about

codes, definitions of variables, variable field locations, frequencies, and any other unique background information. This document will also be deposited into the FITBIR Informatics System to be shared with the TBI research community who access our study data.

To upload data to FITBIR, study staff will download a CSV file for the form structure from the FITBIR Data Dictionary. The subject GUID is entered on the CSV along with the corresponding information that aligns with the data elements in CSV and form structure. Data is then uploaded through the FITBIR web portal. A Data Validation Tool is used on the CSV to ensure data quality, and a data submission tool writes the data to the study in the Repository. Our staff will contact the FITBIR Operations Center to arrange data entry support and to gather information regarding data formatting needs to ensure compatibility with the FITBIR system for uploading. Additionally, we will reach out to the FITBIR Operations Center for assistance in mapping study variables specific to Common Data Elements.

Study participants will be asked if they would like to be re-contacted for future research. During the consenting process, participants will initial the page to indicate that they would like to be contacted in the future; if they choose to decline they will leave that portion of the consent form blank. Participants who meet the eligibility criteria for future studies conducted by the study team may be contacted by phone or email.

Is this a data repository?

Yes **No**

If Yes, provide the name of the Repository

Federal Interagency Traumatic Brain Injury Research Informatics System

Who will have access to the Repository?

The general research community upon request and registration with the system administrators.

What data type will be stored in the Repository?

PHI

LDS

De-identified Data

11.0 Statistical/Data Analysis Plan

11.1 Statistical Considerations:

List the statistical methods to be used to address the primary and secondary objectives, specific aims, and/or research hypotheses. Explain how missing data and outliers will be handled in the analysis. The analysis plan should be consistent with the study objectives. Include any sub-group analyses (e.g., gender or age group). Specify statistical methods and variables for each analysis. Describe how confounding variables will be controlled in the data analysis

1. Data Analyses

The difference between treatment groups sample characteristics including demography, military information and co-variates will be evaluated using Student's 't' and chi-square tests for continuous and categorical variables, respectively. Wilcoxon Rank-Sum test will be used for two-group comparisons where continuous variables are non-normally distributed. We will leverage the statistical power of multilevel modeling to handle missing follow-up data.

Please see section 11.6 for the data analysis plan.

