SAET may also promote recovery at a molecular level. Exercise has been shown to increase brain derived neurotrophic factor (BDNF) (Sleiman et al., 2016), an important biomarker of neuroplasticity and neurogenesis. BDNF is involved in modulating the neuroinflammatory process and promoting neuronal plasticity. The role of BDNF and concussion is also well established. BDNF is known to be diminished following a concussion and has been explored as a diagnostic agent (Korley et al., 2016). Further, given its neuroprotective properties BDNF has also been explored as a treatment option for TBI (Kaplan, Vasterling, & Vedak, 2010). Perhaps given these benefits it is not surprising that SAET has been shown to attenuate the negative impacts of cognitive dysfunction following MTBI by improving processing speed and executive function (Chin, Keyser, Dsurney, & Chan, 2015). A recent meta-analysis offered evidence of the positive effects of resistance training (in isolation of aerobic exercise) on composite cognitive scores, screening measures of cognitive impairment, and executive functioning (Landrigan, Bell, Crowe, Clay, & Mirman, 2020). These findings provide important evidence for the potential compound effect of subthreshold aerobic exercise in conjunction with resistance training in mTBI recovery.

Exercise's effect on mood may offer an alternative supportive mechanism by which exercise can improve mTBI recovery. It is an unfortunate reality that depression, post-traumatic stress disorder, and other mood-related disorders frequently impact SMs and veterans who have had a mTBI (Cole & Bailie, 2016; Stein et al., 2019). In SMs and veterans, the presence of a mood disorder was the strongest predictor of poor long-term outcome as many as 10 years from injury (Lange, French, Lippa, Bailie, & Brickell, 2020). In non-concussed individuals, it has been well documented that regular physical activity benefits individuals with depressive and anxiety symptoms (Pascoe et al., 2020;

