Delis-Kaplan Executive Function System Trail Making (DKEFS TM)	Secondary Aim 1	The DKEFS TM is a paper-and-pencil test consisting of five trials assessing mental flexibility and processing speed (Delis et al, 2001). It is a measure of psychomotor speed, visual search abilities, working memory, and cognitive flexibility. The score on each part of the TMT is determined by the time required to complete each trial. The test has been shown to have good reliability and

		validity when assessing acquired brain injury (Delis et al., 2001).
Delis-Kaplan Executive Function System Color Word (DKEFS CW)	Secondary Aim 1	The DKEFS CW is a measure of inhibition and top-down brain control (Delis et al., 2001). The test has several conditions which require the participant to read words quickly fluidly, name colors, inhibit over-learned responses, and switch between competing tasks. This study will focus on four (i.e., color naming, word reading, inhibition, inhibition/switching). The DKEFS CW task is widely utilized with good psychometric properties and validity for the assessment of individuals with TBI (Delis et al., 2001).
Combat Exposure Scale (CES)	Secondary Aim 1	The Combat Exposure Scale is a 7-item measure used to assess the participants' exposure to combat stress such as enemy fire and in-theater life and death situations (Keane et al., 1989). The 5-point scale for each item is weighted according to severity of exposure. The CES has a coefficient alpha of .85 and a 1-week test re-test of $r = .97$, $p < .0001$.
Post-Traumatic Stress Disorder Checklist (PCL-M)	Secondary Aim 1	The PCL-M is a self-report questionnaire which includes 17 items that are designed to assess symptoms of PTSD (Weathers et al., 1991). The PCL-M is extensively used both in clinical practice and is frequently used in research investigating PTSD and MTBI in military populations (Gerwitz et al., 2010; Belanger et al., 2010). This questionnaire is in the public domain and can be used without copyright restriction. The PCL-M has excellent diagnostic specificity. A conservative cut-off of 45 will be used which is consistent with recommendations from the National Center for PTSD. Empirical evidence suggests that this cut-off is associated with 97% specificity in active duty military (Bliese et al., 2008). Guidelines for assessment of changes for service members with MTBI have been published as well (Belanger et al., 2016).

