Patient Health Questionnaire (PHQ-8)	Secondary Aim 1	The PHQ-8 is a version of the PHQ-9 that omits the question about suicidality. The PHQ-9 is the depression module of the self-administered version of the PRIME-MD diagnostic instrument (PHQ; Kroenke, 2001). The PHQ-9 is an instrument whose items are based on the SDM-IV diagnostic criteria for depression. Each of the 9 items can be scored from 0 (not at all) to 3 (nearly every day). Its validity and reliability as a diagnostic measure as well as its utility in assessing depression severity and monitoring treatment response are well-established (Lowe et al., 2004). It also has demonstrated reliability and validity for diagnosing depression in patients with MTBI (Fann et al., 2005). This questionnaire is in the public domain and can be used without copyright restriction.
Patients' Global Impression of Change (PGIC) Scale	Secondary Aim 1	The self-report measure Patient Global Impression of Change (PGIC) reflects a patient's belief about the efficacy of treatment. Although widely used in chronic pain clinical

		trials, PGIC's validity has not been formally assessed. PGIC is a 7 point scale depicting a patient's rating of overall improvement.
Pittsburgh Sleep Quality Inventory (PSQI)	Secondary Aim 1	A self-rated questionnaire which assesses sleep quality and disturbances over a 1- month time interval. It measures subjective sleep quality, sleep latency, sleep duration, habitual sleep efficiency, sleep disturbances, use of sleep medication, and daytime dysfunction over the last month. The PSQI takes approximately 3 minutes to administer.
Key Behaviors Change Inventory (KBCI)	Secondary Aim 1	The KBCI is a 64-item questionnaire that assesses behavioral areas such as lack of motivation, difficulties communicating, lack of insight into difficulties, and relationship problems (Kolitz et al., 2003). The instrument has good content and construct validity and an internal consistency reliability of 0.82-0.91.
Blast Exposure Threshold Study (BETS)	Secondary Aim 1	The BETS is a self-report survey that was designed to assess occupational blast exposure from military personnel. The standardized measurement tool efficiently records and calculates cumulative, life-long exposure to potential sources of blast overpressure. The BETS development was supported by the JPC-5 Exposure Standards Working Group and will be included in our study in order to better understand blast exposure history relative to outcome from CR in mTBI.

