11.5 Please provide a justification for your sample size

With 140 participants, 70 in each intervention arm, we will be able to potentially detect a significant difference in change in neurobehavioral symptoms between the two physical activity interventions (i.e., SAET and SCG) with an 85% power using a two-tailed test and an alpha of 0.05. This estimate is based on similar research on a civilian population (Kaplan, Vasterling, & Vedak, 2010), and takes into consideration a 20% attrition. The 140 participants recruited will suffice to address the research question for secondary aims given the same parameters.

11.6 Data Analysis Plan Complete description: Background, Objectives, Design, Step by Step how the project is going to be done

Primary Aim: Neurobehavioral symptoms: Primary analyses will evaluate whether change in neurobehavioral symptoms from pre- to immediate post-treatment, as well as from immediate post-treatment to 3 months post-treatment, differ between the physical activity interventions. In addition to assessing change in symptoms continuously, we will also evaluate reaching a clinically-relevant change in neurobehavioral symptoms (defined as a change in NSI score of 8 points) (Belanger et al., 2016). Secondary analyses will investigate differences in overall change in neurobehavioral symptoms from pre-treatment to 3 months post-treatment between the interventions using multilevel mixed-effect modeling. This approach will take into consideration between-subject variance based on randomized group, as well as within-subject variance for repeated measures. Analyses will be based on intention to treat (ITT).

Sub-Aim 1: Cognitive Performance: Similar statistical approach as Aim 1 will be conducted for Sub-Aim 1. Exposure will remain as the type of intervention (i.e. SAET vs. SCG); however, outcome will be on global deficit score based on the cognitive test scores.

Sub-Aim 2: Physiological Adaptation: Analysis of Variance (ANOVA) will be utilized to determine differences in continuous variables of physiological adaptation (i.e., cerebrovascular flow, improved cardiovascular health) between interventions.

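### Covariates are handled only by significance tests of baseline differences between randomized arms; prespecified adjustment for baseline mood scores already collected would serve the primary NSI analysis better

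*Protocol*

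**What the plan says.** The form text at the head of Protocol section 11.1 asks, among other things, how confounding will be dealt with in the analysis. The reply has one sentence on covariates: differences between arms in "sample characteristics including demography, military information and co-variates will be evaluated using" Student's t and chi-square tests, with the Wilcoxon rank-sum test for non-normal continuous variables. It then refers to section 11.6.

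Section 11.6 describes the primary NSI analysis as a comparison of change between arms, with a mixed model that accounts for randomized group and repeated measures. ANOVA is named for sub-aim 2 and the M-ADL, and Poisson regression for the CFT. No baseline covariate is named in any of these, and nothing says what follows if a baseline test is significant.

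Elsewhere the protocol identifies a prognostic variable. Section 9.2 states that in service members and veterans "the presence of a mood disorder was the strongest predictor of poor long-term outcome", over a horizon of up to 10 years. Section 10.2 lists the PCL-M, with "17 items that are designed to assess symptoms of PTSD", and the PHQ-8, of whose parent instrument it says that "its utility in assessing depression severity and monitoring treatment response are well-established". Section 10.1 places the evaluations before treatment, after treatment and 3 months later. Depression, anxiety and PTSD diagnoses are also requested from medical records. Randomization uses blocks of 6, with no stratification factor named.

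**The concern.** In a randomized comparison any baseline difference between arms is due to chance, so a test of that difference addresses a null hypothesis already known to be true. Its p-value does not show whether the variable affects the NSI. A variable can be significantly imbalanced and irrelevant, or non-significantly imbalanced and important.

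The variable that the protocol itself singles out as prognostic is measured before treatment but protected neither by stratification nor by the analysis as described. What is at stake is precision, and protection against an unlucky allocation, in the primary NSI comparison. Validity is not at stake.

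**Working it through.** **Inputs from the protocol (section 11.5).** "With 140 participants, 70 in each intervention arm"; "with an 85% power using a two-tailed test and an alpha of 0.05"; the estimate "takes into consideration a 20% attrition". No effect size or SD is given, only a source: "This estimate is based on similar research on a civilian population". The 85% therefore cannot be reproduced; only the standardized difference that it implies can be back-solved.

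**Assumed, because the protocol gives no figure.** Correlation r of baseline mood with NSI change: 0.3 to 0.5. Share R² of residual NSI variance explained by mood: 5% to 15%. The R² range lies below the squares of those correlations (0.09 to 0.25) because baseline NSI, which enters through the change score, probably carries part of the mood effect.

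**1. Implied detectable difference.** Completers per arm: 70 × 0.80 = 56. With a normal approximation, d = (1.960 + 1.036) × √(2/56) = 0.566 SD.

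**2. What a baseline test does with a realized imbalance.** At 70 per arm the standard error of a standardized baseline difference is √(2/70) = 0.169.
- An observed 0.3 SD difference gives z = 0.3/0.169 = 1.77, two-sided p about 0.08. It is not flagged at 0.05.
- The same calculation gives how often chance produces an imbalance of at least that size on one variable, in either direction: about 8% of trials.
- Only observed differences above 1.96 × 0.169 = 0.33 SD are flagged.

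**3. Shift in the contrast given that imbalance.** Shift = r × imbalance, in SD of NSI change.
- r = 0.3: 0.3 × 0.3 = 0.09 SD, which is 0.09/0.566 = 16% of the implied detectable difference.
- r = 0.5: 0.5 × 0.3 = 0.15 SD, which is 0.15/0.566 = 26%.

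**4. False flags.** With k independent tests at 0.05, P(at least one) = 1 − 0.95^k: 40% for k = 10 and 64% for k = 20. Correlated characteristics, such as age, rank and education, would change these figures, so they are only a guide.

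**5. Power after adjustment.** Power = Φ(0.566/√(1 − R²)/√(2/56) − 1.96).

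| R² (assumed) | Power |
|---|---|
| 0 | 85% |
| 0.05 | 87% |
| 0.10 | 88% |
| 0.15 | 90% |

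If the full correlation applied with nothing absorbed by baseline NSI, r = 0.3 would give 88.1% and r = 0.5 would give 93.3%. The second figure is an upper bound rather than an expectation.

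**The case against.** The strongest reply is that a covariate list is ordinary SAP content. An SAP may exist, and the protocol rules out no adjustment. That stands: a missing list alone would be no finding. The point rests on what the protocol does state, namely baseline significance testing as its whole answer on confounding, and models described without covariates although a named prognostic variable is collected.

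A second reply is that the baseline tests change no estimate. That also stands. Deleting them is good practice, but the gain comes from the adjustment.

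A third is that the prognostic statement concerns long-term outcome, while the endpoint here is NSI change over about 8 weeks and then to 3 months after treatment. The NSI also contains affective items, and analysing change already uses baseline NSI. This is fair, and it is why the low end of the assumed ranges is the more likely.

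Four stronger readings are tempting, and the documents do not support them.
- A reader might infer that the unadjusted result is biased. It is not: randomization keeps the estimator unbiased and its standard error covers chance imbalance. The figures in step 3 are shifts conditional on one unlucky allocation.
- A reader might infer that baseline p-values will select covariates. The protocol attaches no consequence to these tests. It leaves that open but does not plan it.
- A reader might say that a 0.3 SD imbalance would be flagged 42% of the time. That is the power against a true population difference of 0.3 SD, which randomization excludes. A realized 0.3 SD difference is simply not significant.
- A reader might take mood disorder to be the strongest predictor of outcome in general. The protocol says so only of long-term outcome.

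**Conclusion.** The point holds as a moderate improvement to the analysis; it is not a threat to validity. Section 11.1 offers an uninformative procedure where it was asked about control of confounding, and section 11.6 as written leaves prognostic baseline scores unused. The unadjusted comparison is valid.

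The cost is some precision: about 2 to 5 percentage points of power under the assumed R² of 5% to 15%. In addition, a chance imbalance of a size seen in about 8% of trials would go uncorrected, with a shift of 0.09 to 0.15 SD under the assumed correlations. All of these sizes depend on correlations that the protocol does not give. The 0.566 SD yardstick is back-solved from the stated power and attrition, not taken from the protocol.

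**What to change.** **Section 11.1.** Replace the between-arm significance tests with descriptive baseline summaries by arm, without p-values.

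**Section 11.6.** Prespecify baseline PCL-M and PHQ-8, alongside baseline NSI, as covariates in the primary NSI model whatever their observed balance, and state that no covariate will be chosen from baseline tests. If pre-treatment NSI is kept as an outcome in the mixed model, it should not also be entered as a covariate, and the mood scores should interact with visit so that they adjust the change contrast.

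**Cost.** A few sentences and no new data collection. The covariates use a few degrees of freedom out of about 112 completers (2 × 56). The plan would also need a stated rule for missing baseline scores, so that adjustment does not drop randomized participants from the intention-to-treat analysis.
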